8.3.1 When and How to Withdraw Subjects

A subject may end his or her participation in the study at any time. If a subject withdraws, the Principal Investigator will make a reasonable effort to determine the reason for the withdrawal from the study and to complete termination procedures as described in [section 8.5.2](#) and [section 8.5.4](#). Telephone calls, registered letters, and email correspondence are considered reasonable

effort. For subjects leaving the study, a targeted examination may be performed, if medically indicated and if permitted by the subject.

A subject may be withdrawn for an AE or SAE resulting in a safety concern. When a subject withdraws due to an AE or is withdrawn by the principal investigator due to an AE, the sponsor's safety office, the USAMRMC Clinical Services Support Division (CSSD), Product Safety Surveillance Branch (PSSB), must be notified within 72 hours ([contact]). The Principal Investigator must follow specific policy regarding the timely reporting of AEs and SAEs to the US Investigational IRB as the IRB of record ([section 11.5.1.2](#)). In all cases, the Principal Investigator will make a reasonable effort to complete study termination procedures.

If a subject meets withdrawal conditions for a concomitant medication violation or noncompliance, this should clearly be stated in the source document and the study termination eCRF.

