6.1.2. Study Exposure

The baseline visit will be at Visit 3, Day 0, and the first dose of the study medication will be administered after randomization, determination of the baseline QHT score, and tooth polishing. The study exposure, in days, will be measured from Day 0 (date of randomization) to the last day

the subject was in the study. For subjects completing Visit 4, Day 4, the exposure will be 4 days (counting Day 0), regardless of whether the subject took any of the self-administered treatment. For early withdrawal subjects the study exposure will be from Day 0 to (and including) the subject's last day when the subject informs the study site of their early withdrawal. If the subject is lost to follow-up, the study site personnel will attempt to contact the subject to determine the day when they stopped study participation, and any adverse events that occurred during their self-administration time. Randomized subjects who are lost to follow-up and who are unable to be contacted will be assigned one day of study exposure, namely Day 0.

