6.2.4.4. Recording Adverse Events

Methods/Timing for Assessing, Recording and Analyzing Safety Measurements (Endpoints)

AEs and SAEs will be assessed at each study visit and documented in the source records. All AEs will be recorded on the eCRFs using accepted medical terms and/or the diagnoses that accurately characterizes the event. SAEs will be documented using the SAE paper form. It should be noted that the form for collection of SAE information is not the same as the AE eCRF. Where the same data are collected on both forms, the forms must be completed in a consistent manner. For example, the same event term should be used on both forms.

When a diagnosis is known, the AE term recorded on the eCRF will be the diagnosis rather than a constellation of symptoms. The investigator will assess and record for all AEs/SAEs: a description of the event (if the event consists of a cluster of signs and symptoms, a diagnosis should be recorded rather than each sign and symptom): onset date and time, and resolution date and time: intensity (recorded as mild, moderate or severe): relationship to study drug (recorded as unrelated, unlikely related, possibly related, probably related and definitely related): outcome (recorded as recovered, recovering, resolved with sequelae, not resolved, fatal, ongoing (end of study) or unknown if applicable): action taken with the study product (recorded as no action taken, dose reduced, interrupted, discontinued). When an event has not resolved by study closure, it will be documented on the AE eCRF as "ongoing."

The timeframe for the collection of AEs and SAEs for each subject begins at the first administration of investigational product (Visit 3, Day 0) through Visit 4, Day 4.

Duration of Follow-Up of Subjects after Adverse Events

Investigators are required to follow SAEs to resolution, even if this extends beyond the prescribed reporting period. Resolution is the return to baseline status or stabilization of the condition with the probability that it will become chronic. The SAE outcomes will be reported to the sponsor's representative using the Serious Adverse Event Report Form.

Investigators are not obligated to actively seek SAEs in former subjects; however, if an SAE, considered to be related to the investigational product is brought to the attention of the investigator *at any time* following completion of the study, the event will be reported to the

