7.1. Primary (Safety) Analyses

7.1.1. Adverse Events

A subject listing of deaths, other serious AEs, and discontinuations due to adverse events will be presented in tabular form by treatment received. Information will include a description of the event, the study day when the event was first observed, severity if applicable, relationship to study drug, resolution status of the event, subject status within the study (if applicable).

Summaries of adverse events by SOC only, and by event severity will be given by study arm. Separate tabular summaries by study arm, system organ class (SOC) and by preferred term (PT) within SOC will be given for:

- All AEs
- AEs possibly, probably, definitely related to study medication.

For each SOC and SOC, PT combination the estimated incidence proportions and estimated incidence rates will be given by treatment received.

The incidence proportion will be calculated as the number of subjects with a given treatment (KSL-W, placebo) having at least one AE with that SOC or SOC-PT classification, divided by the number of subjects with that treatment (expressed as a percent).

The incidence rate will be calculated as the number of adverse events with that SOC or SOC-PT classification divided by the total study exposure from all subjects with a given treatment. The study exposure is determined in days (see 3.1.2), but the total study exposure will be converted to subject-weeks. The total number of events and the rate in events per subject-week will be given. Since incidence rate takes into account exposure, this may be the measure more applicable to combine with other studies.

Subject listings of adverse events will include the verbatim AE terms as well as the SOC, PT. Severity, relationship with study drug, resolution of the event, and ongoing status of the subject within the study will also be shown in the subject listings, which will be presented by treatment and subject within treatment.

Adverse event data collected on paper forms will be described in the final Clinical Study Report and not displayed in a table or listing. This will include any additional maternal or paternal adverse events which will be collected on the Pregnancy Surveillance Form as well as any data collected on the Serious Adverse Event Form.

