Last follow-up : See SAP section 3.1.2 pgs 11-12. If subject completed the study then the last date is the date of Day 4 visit (VISITDT, pg 73 eCRF). If early withdrawal then last date is STATUS.WDRAWDT, pg 97 eCRF)

Adverse events from AES, page 100 eCRF tables and listings would come from ADaM adae after MeDRA coding.

TREF12

Summary of Serious Adverse Events , Discontinuations Due to Adverse Events, Deaths, Safety Population: KSL-W (N=xx), Placebo (N=xx)

	KSL-W	Placebo	Total
Number (%) of Subjects With Serious Adverse Events	xx (xx.x%)	xx (xx.x%)	xx (xx.x%)
Number (%) of Discontinuations Due to Adverse Events			
Number (%) of Deaths			

Subject listing of deaths, SAE's, and adverse event discontinuations: LREF16a, LREF16b
events from AES, page 100 eCRF tables and listings would come from ADaM adae after MeDRA coding.

Table TREF13

**Summary of Adverse Event Proportion, Rate by System Organ Class
All Treatment Emergent Adverse Events
Safety Population: KSL-W (N=xx), Placebo (N=xx)**

System Organ Class	KSL-W		Placebo			
	Number (%) [*]	Number of Events ^{**}	Event Rate (evt/sbj-wk) ^{***}	Number (%)	Number of Events	Event Rate (evt/sbj-wk)
xxxxx	xx (xx.x%)	xx	x.xx	xx (xx.x%)	xx	x.xx
xxxxx						

^{*}Number of subjects, n, with at least one event, and % is 100 n/N.

^{**}Total number of events from the given category

^{***}Total number of events divided by the total study exposure.

Subject listing: LREF16a

TREF14

Summary of Adverse Event Proportion, Rate by System Organ Class and Preferred Term
All Treatment Emergent Adverse Events
Safety Population: KSL-W (N=xx), Placebo (N=xx)

System Organ Class	Preferred Term	KSL-W			Placebo		
		Number of Subjects (%)*	Number** of Events	Event Rate (evt/sbj-wk)***	Number of Subjects (%)	Number of Events	Event Rate (evt/sbj-wk)
xxx	(Total)	xx (xx.x%)	xx	x.xx	xx (xx.x%)	xx	x.xx
	xxxx						
	xxxx						
	xxxx						
xxxxx	(Total)						
	xxxxx						
	xxxxx						

*Number of subjects, n, with at least one event, and % is 100 n/N.

**Total number of events from the given category

*** Total number of events divided by the total study exposure.

Subject listing LREF16a

Events from AES, page 100 eCRF tables and listings would come from ADaM adae after MeDRA coding0 eCRF and total exposure for event rate

TR^EF15

Summary of Adverse Event Proportion, Rate by Event Severity Safety Population: KSL-W (N=xx), Placebo (N=xx)

Severity	KSL-W		Placebo	

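### Exposure for early withdrawals has no Day 4 cap in SAP 6.1.2, and the TREF11 note does not carry the lost-to-follow-up rules, so the AE rate can rest on a wrong or ambiguous denominator

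*SAP*

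**What the plan says.** SAP 6.1.2 (Study Exposure) sets four rules:

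- **Completers:** "For subjects completing Visit 4, Day 4, the exposure will be 4 days (counting Day 0"), whether or not the self-administered gum was taken.
- **Early withdrawals:** from Day 0 up to and including the "last day when the subject informs the study site of their early withdrawal". No latest day is given.
- **Lost to follow-up, contacted:** the site tries to "determine the day when they stopped study participation", and asks about AEs during the self-administration period.
- **Lost to follow-up, not contacted:** subjects who are "unable to be contacted will be assigned one day of study exposure, namely Day 0".

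Under SAP 6.2.4.4, AE collection "begins at the first administration of investigational product (Visit 3, Day 0) through Visit 4, Day 4". Under SAP 7.1.1, the rate is the number of events "divided by the total study exposure from all subjects with a given treatment", converted to subject-weeks. The same section says this rate may be the better measure for combining with other studies.

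The programming note under the TREF11 shell (SAP 11.2) refers the programmer to SAP section 3.1.2 for last follow-up. It uses the Day 4 visit date for completers and then says: "If early withdrawal then last date is STATUS.WDRAWDT, pg 97 eCRF". This SAP has no section 3.1.2; the exposure rules are in 6.1.2. SAP 7.1.1 contains the same wrong reference.

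The synopses of both documents class a subject as lost to follow-up when the Day 4 morning evaluation is more than 24 hours late.

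**The concern.** An event rate needs a numerator and a denominator that cover the same period. Here the numerator closes at the Day 4 visit, but the denominator for an early withdrawal closes whenever the subject tells the site. Notice on or after Day 4 gives a non-completer more exposure than a completer, and from Day 5 the extra days lie outside the stated AE window.

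The second problem is that a lost subject's exposure depends on which instruction the programmer follows. The rules for lost subjects appear only in SAP 6.1.2, which the TREF11 note does not correctly cite. The shells make it easy to treat a lost subject as an early withdrawal: TREF01 lists loss to follow-up among the reasons for early discontinuation, and LREF13 offers only a completion date or a withdrawal date.

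AE incidence is the primary endpoint (Protocol 7.1), and TREF11 and TREF13 to TREF16 all report rates based on study exposure. Unlike the fixed 4 days, which applies to every completer in both arms, these rules act only in an arm that has dropouts.

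**Working it through.** **Inputs.** Arms of 13, from 26 enrolled to obtain 24 completers (Protocol 5.7). The plan therefore allows for 26 − 24 = 2 non-completers, or 2/26 = 7.7%, about one per arm. Exposure rules are from SAP 6.1.2, the AE window from SAP 6.2.4.4 and the 24-hour rule from the synopses. The documents give no notification days, so those below are assumptions.

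**Step 1: the plan's own figure.** Day 4 − Day 0 = 4 days, and Day 0 to Day 3 inclusive = 4 days. Both reproduce the stated 4. Day 0 to Day 4 inclusive = 5 does not. The inclusive count prescribed for early withdrawals therefore gives 5 days to a subject who gives notice on Day 4, one more than a completer.

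**Step 2: one early withdrawal in an arm of 13, notice on Day k.**

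- As written: D = 4 × 12 + (k + 1)
- With a 4-day cap: C = 48 + min(k + 1, 4)
- Understatement of the rate = 1 − C/D

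| Notice | D (days) | C (days) | Rate too low by |
|---|---|---|---|
| Day 2 | 51 | 51 | 0% |
| Day 3 | 52 | 52 | 0% |
| Day 4 | 53 | 52 | 1 − 52/53 = 1.9% |
| Day 5 | 54 | 52 | 1 − 52/54 = 3.7% |

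For illustration, 5 AEs in that arm give 5/(52/7) = 0.673 per subject-week with the cap. As written they give 5/(53/7) = 0.660 for Day 4 notice and 5/(54/7) = 0.648 for Day 5.

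**Step 3: sensitivity to the day convention.** If the AE window is counted as five calendar days and the withdrawal is capped at 5, the Day 4 excess disappears. The Day 5 understatement becomes 1 − 53/54 = 1.9%.

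**Step 4: SAP 6.1.2 against TREF11 for one uncontactable lost subject.** This assumes that the subject is programmed as an early withdrawal and that STATUS.WDRAWDT holds the date on which lost status is recorded. Under the 24-hour rule that is Day 5 at about the earliest. The TREF11 footnote measures from randomization to last follow-up, so the date difference is 5.

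- SAP 6.1.2: 48 + 1 = 49 days
- TREF11 note: 48 + 5 = 53 days
- Rate ratio for the same events: 49/53 = 0.925, so 7.5% lower under TREF11

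**Step 5: what does not change.** The incidence proportion divides by the number of subjects, so exposure does not enter it.

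**The case against.** The strongest objection is the 24-hour rule. A subject who stops chewing on Day 1, misses Day 4 and calls on Day 10 looks like an 11-day exposure under SAP 6.1.2. On the natural reading, however, that subject is already lost to follow-up by about Day 5 and is counted to the day participation stopped. A reader might infer understatements of 7.1% for one subject giving notice on Day 7, or 17.5% on Day 14. The documents do not support those sizes unless a late no-show escapes the rule. Its wording concerns a late evaluation, so applying it to a no-show is a reading, but the obvious one.

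The TREF11 note does point to the SAP's exposure section, though by a wrong number, and its early-withdrawal sentence can be read as excluding lost subjects. The documents do not define STATUS.WDRAWDT. Protocol 8.3.1 counts "Telephone calls, registered letters, and email correspondence" as reasonable effort, from which a reader might infer that the field holds the date on which the site gave up. It could equally hold the last day of participation. The ambiguity stands; any particular size for it is conditional.

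The direction is also mixed. Giving an uncontactable subject 1 day raises the rate (52/49 = 1.061, or 6.1% higher). Completers contribute 4 days to a window that touches five calendar days, which raises it by a factor of up to 5/4 = 1.25. A reader might also infer that the less tolerable gum would look safer. The documents give no support for that: none of the six withdrawals described from the 28-day Phase 2a study (Protocol 5.5.2) was attributed to an AE.

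Finally, AE collection might stay open for withdrawn subjects, because Protocol 8.3.4 seeks a termination visit without a date limit. Protocol 8.3.2 only reports data collected up to withdrawal, however, and neither section extends the window in SAP 6.2.4.4.

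**Conclusion.** The point holds in a limited form. For early withdrawals, SAP 6.1.2 sets an uncapped end date that matches neither the AE window nor the completer count. With one such subject in an arm of 13, the rate is 1.9% too low for notice on Day 4 and 3.7% too low for notice on Day 5, against a 4-day cap. There is no effect for notice by Day 3.

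The mismatch with TREF11 is separate. It is worth 7.5% for one uncontactable subject, if lost subjects are programmed as early withdrawals and the withdrawal date is about Day 5.

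It would be wrong to conclude that exposure is inflated for all non-completers, since SAP 6.1.2 limits lost subjects to their stop day or 1 day. It would also be wrong to conclude that the rate will be understated: that needs notice on or after Day 4, or the assumed reading of the TREF11 note. The effect is small, but it falls on a primary safety measure and is easily removed.

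**What to change.** **SAP 6.1.2.** End every non-completer's exposure on the last day through which AE status was actually obtained. Count days as for completers (Day 0 is the first day) and cap the total at the completer value of 4. Keep the 1-day assignment for lost subjects who cannot be contacted. Do not substitute the day participation stopped: a subject who stops on Day 1 and reports AE status on Day 3 would lose observed days while any events on those days stayed in the numerator.

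**TREF11 note.** Replace the STATUS.WDRAWDT sentence with this rule, including the 1-day assignment, and correct the section reference to 6.1.2. Make the same correction in SAP 7.1.1. TREF11 and TREF13 to TREF16 then share one denominator.

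**Cost.** A few sentences in the SAP and one programming note, settled before database lock and unblinding. No new data are needed. The downside is a slightly smaller denominator, and so a slightly higher printed rate, in an arm with dropouts.

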6.2. Specification of Safety Measurements (Endpoints)

6.2.1. Vital Signs

Vital signs measurements include blood pressure (systolic and diastolic), heart rate, respiration rate, and body temperature. These measurements will be collected after the subject has been seated for at least 5 minutes during screening and on Day 0 and Day 4.

6.2.2. Physical Examination

During the screening visit a physical examination will be performed. A brief symptom-oriented physical exam will be performed on Day 4 and will involve observation of the physical appearance of the subject. Any unexpected abnormalities or changes from baseline will be assessed and documented. Findings that are considered to be of clinical significance will be recorded as AEs.

6.2.3. Intraoral Examination

6.2.3.1. Oral Soft Tissue Examination

The OST examination will be performed by visually inspecting the oral cavity and perioral area using a dental light, dental mirror, periodontal probe and gauze. Any abnormalities at baseline will be recorded in order to detect changes such as the development of erythema, ulceration, or tissue sloughing should they occur during the four day study period.

The structures examined will include the labial mucosa (including lips), buccal mucosa, mucogingival folds, gingival mucosa, hard palate, soft palate, tonsillar area, pharyngeal area, tongue, sublingual area, submandibular area, salivary glands, temporomandibular joint, and any other area as deemed necessary by the investigator. The same examiner will conduct the subject's OST during the study.

OST observations will be listed as "Normal" or "Abnormal." Abnormal observations will be documented and described in the subject's study records. Any changes will be recorded, severity assessed according to standard dental examination procedures, and a decision made with respect to whether or not these changes are related to treatment with the study drug. New or worsened OST findings occurring after the first use of the study product will be recorded as AEs.

6.2.3.2. Oral Hard Tissue Examination

The OHT examination will assess irregularities in tooth enamel, tooth fracture, decay, faulty restorations and implants. OHT observations will be listed as “Absent” or “Present” and any “Present” observations will be described.

6.2.4. Adverse Event Determination and Assessment

6.2.4.1. Adverse Event or Suspected Adverse Reaction

An AE is any untoward medical occurrence associated with the use of a drug in humans, whether or not considered drug related.

Suspected adverse reaction means any AE for which there is a reasonable possibility that the drug caused the AE. For the purposes of IND safety reporting, “reasonable possibility” means there is evidence to suggest a causal relationship between the drug and the AE. Suspected adverse reaction implies a lesser degree of certainty about causality than adverse reaction, which means any AE caused by a drug.

Treatment-emergent AEs is defined as any AE that occurs on or after administration of the first dose of study treatment (Day 0) or any medical or dental condition that is present at baseline (Day 0) but worsens in intensity subsequent to the administration of the first dose of study treatment.

Solicited Adverse Event

This section is not applicable.

Serious Adverse Event or Serious Suspected Adverse Reaction

An AE or suspected adverse reaction is considered “serious” if, in the view of either the investigator or sponsor, it results in any of the following outcomes:

- Death
- Life-threatening AE
- In-patient hospitalization or prolongation of existing hospitalization
- Persistent or significant incapacity or substantial disruption of the ability to conduct normal life functions
- Congenital anomaly/birth defect.

An AE or suspected adverse reaction is considered “life-threatening” if, in the view of either the investigator or sponsor, its occurrence places the patient or subject at immediate risk of death. It does not include an AE or suspected adverse reaction that, had it occurred in a more severe form, might have caused death.

Important medical events that may not result in death, be life-threatening, or require hospitalization may be considered serious when, based upon appropriate medical judgment, they may jeopardize the patient or subject and may require medical or surgical intervention to prevent one of the outcomes listed in this definition. Examples of such medical events include allergic bronchospasm requiring intensive treatment in an emergency room or at home, blood dyscrasias

or convulsions that do not result in inpatient hospitalization, or the development of drug dependency or drug abuse.

Unexpected Adverse Event or Unexpected Suspected Adverse Reaction

An AE or suspected adverse reaction is considered “unexpected” if it is not listed in the investigator brochure or is not listed at the specificity or severity that has been observed; or, if an investigator brochure is not required or available, is not consistent with the risk information described in the general investigational plan or elsewhere in the current application, as amended. For example, under this definition, hepatic necrosis would be unexpected (by virtue of greater severity) if the investigator brochure referred only to elevated hepatic enzymes or hepatitis. Similarly, cerebral thromboembolism and cerebral vasculitis would be unexpected (by virtue of greater specificity) if the investigator brochure listed only cerebral vascular accidents. “Unexpected,” as used in this definition, also refers to AEs or suspected adverse reactions that are mentioned in the investigator brochure as occurring with a class of drugs or as anticipated from the pharmacological properties of the drug, but are not specifically mentioned as occurring with the particular drug under investigation.

Unanticipated Problems Involving Risks to Subjects or Others

Federal regulations require that unanticipated problems that are serious adverse events involving risks to subjects or others be promptly reported to the IRB within 5 business days of the investigator becoming aware of the event. Any other unanticipated problem should be reported to the IRB within 10 days of the investigator becoming aware of the problem. These events encompass a broader category of events than SAEs and may include issues such as problems with loss of control of subject data or the investigational product; adverse psychological reactions; or breach of confidentiality. Risks to others (e.g., program personnel) must also be reported.

Unanticipated problems involving risks to subjects or others are any incident, experience, or outcome that meets all of the following criteria:

- Unexpected (in terms of nature, severity, or frequency) given (a) the procedures that are described in the protocol, investigator brochure or informed consent document; and (b) the characteristics of the subject population;
- Related or possibly related to a subject’s participation in the study; and
- Suggests that the study places subjects or others at a greater risk of harm than was previously known or recognized.

The IRB and/or the ORP will evaluate the Principal Investigator’s and Research Monitor’s reports to determine whether a given incident, experience or outcome constitutes an unanticipated problem involving risk to subjects or others and, in coordination with USAMRMC CSSD, ensure reporting of the unanticipated problems involving risk to subjects or others to the appropriate regulatory offices, as applicable.

